4.1. Risk Category and Rationale (US Only)

The SenoClaire® - GE Breast Tomosynthesis (DBT) and mammography devices under investigation are considered non-significant risk devices per the 21 CFR 812. 3 definition:

- 1) it is not intended as an implant;
- 2) it is not purported or represented to be for a use in supporting or sustaining human life;
- 3) it is not for a use of substantial importance in diagnosing, curing, mitigating, or treating disease, or otherwise preventing impairment of human health;
- 4) and it does not otherwise present a potential for serious risk to the health, safety, or welfare of a subject.

This designation of non-significant risk is supported by the study design in which DBT data will not be used as the sole measure of diagnosis without distinct confirmation from conventional methods, such as mammography or other standard of care procedures (e.g., breast ultrasound, breast magnetic resonance imaging (MRI), or biopsy) at the investigational site.

4.2. Device Classification and Rationale

In the United States (US) and France, the SenoClaire® - GE Breast Tomosynthesis (DBT) is considered to be Class III, as defined by the US FDA CFR 1020.30-33 and French National Agency for the Safety of Medicine and Health Products regulations in accordance with the European Medical Directive 93/42/EEC. FFDM devices without tomosynthesis or computed tomography breast imaging devices are considered to be Class II and Class IIa (special controls), as defined by the US FDA 21 CFR 892.1715 and French National Agency for the Safety of Medicine and Health Products regulations in accordance with the European Medical Directive 93/42/EEC.

The IDI MammoWorkstation is a Class II medical device under 21 CFR 892.2050 Picture Archiving and Communications Systems (product Code LLZ) and Class IIa (special controls) in Europe.

4.3. Device Issuance and Replacement

SenoClaire® - GE Breast Tomosynthesis (DBT), FFDM, and IDI MammoWorkstation devices used in this study will be commercially available. Unique identifying information (e.g. model, serial number, etc.) of each device used in this study will be recorded.

Ancillary equipment, including safety equipment such as protective vests, and surgical equipment necessary for biopsy(ies) procedure(s) will be used in this study according to the standard of care at the investigational site. These devices will be owned and maintained by the investigational site.

Sites will be encouraged to use equipment owned by the site, if available. For sites that do not own required mammography equipment (DBT, FFDM, and/or IDI MammoWorkstation) or component software versions necessary to complete study procedures, the Sponsor may provide devices for study use.

4.3.1. Maintenance of Research Devices

Devices used in this study will be maintained, calibrated, and ensured to be functioning correctly during the study, in accordance with applicable site policy and state and federal requirements. The Site Principal Investigator (PI) should inform the Sponsor of any known or anticipated issues with device functionality or availability that could impact the conduct or outcomes of this research study.

4.3.2. Concurrent Use of Research Devices

The DBT and FFDM devices used in this study are commercially available, multiple-use devices. Devices owned by the site may be used concurrently in this research and for standard of care procedures outside of this study. Devices provided to the site by GE shall be limited to use only for this protocol. The site is responsible for completing routine care, such as prevention of cross-contamination, between procedures that could impact study subjects.

4.3.3. Device Software and Configuration Management

The most current commercial configuration and software version for SenoClaire[®] - GE Breast Tomosynthesis (DBT) will be used during this study, and the site(s) should use an IDI MammoWorkstation with software version 4.7 MR2 or higher (capable of viewing V-Preview images). In the event of commercial release of software versions or configuration changes that will be implemented on devices used in this study, changes shall not increase risk classification of the study. The Site Principal Investigator (PI) is responsible for notifying the Sponsor of any current or planned software or configuration changes, including the date of implementation on a per-device basis. The Sponsor may, at its discretion or upon site request, require additional training or quality control procedures (e.g. calibration or other routine engineering maintenance activities) following software or configuration changes.

4.4. Disposition of the Device/Product

Devices and associated accessories, provided to the site for the purposes of this clinical trial, will be collected at the end of the study and returned to GE Healthcare.

5. OBJECTIVES OF RESEARCH STUDY

5.1. Hypothesis

No statistical hypothesis is tested in this data collection study. The sample size for breast biopsy subjects in this study is determined to provide sufficient accrual of cancer cases for a subsequent statistically powered analysis as part of a separate protocol (ADAPT-BIE).

5.2. Study Objectives

5.2.1. Primary Objective(s)

The aim of this recruitment plan (ADAPT-BX) is to collect image and technical data on both digital breast tomosynthesis (DBT) and full-field digital mammography (FFDM), along with other subject data, including histology results from biopsy specimen examination and cancer classification data, from initially asymptomatic women referred for biopsy after recall from screening and diagnostic work-up. These data will be included in a subsequent and prospectively planned pooled analysis described in a separate protocol (ADAPT-BIE) examining superiority of DBT to FFDM for breast cancer diagnosis and other clinical performance measures.

5.2.2. Characteristic Objectives

An exploratory aim is to describe cancer and non-cancer cases identified in this accrual study based on histology findings and lesion type.

5.3. Study Endpoints

5.3.1. Primary endpoints

The primary endpoint will be the respective site's diagnosis for each subject of cancer status (positive or negative/benign) based on histology of biopsy/surgical findings and histologic concordance with imaging for benign lesions.

5.3.2. Characteristic Endpoints

Characteristic endpoints for all subjects will include histology findings and size, lesion type, and other lesion characteristics based on image appearance. Technical characteristics of electronic image data collected from subjects, such as information related to radiation dose, may be extracted and analyzed by the Sponsor for the purposes of this study.

5.3.3. Safety endpoint

Device-related adverse events (AEs), serious adverse events (SAEs), and device malfunctions by overall occurrence and imaging modality (DBT and FFDM) that occur during the study will be collected. No other clinical safety assessments will be performed.

6. DESIGN OF RESEARCH STUDY

[figure not shown]
6.1. Type of Research Study

6.1.1. Study Type

This study (ADAPT-BX) is an open-label, multi-center, within-subject crossover, prospective, clinical research study, collecting images and associated data from bi-lateral two-view DBT and FFDM exams conducted with GE systems. Study subjects will be initially asymptomatic adult women ≥ 30 years of age presenting for breast biopsy based on prior breast imaging.

The data from this study will be pooled with data from other subjects, who will have been recruited under other GEHC protocols (including ADAPT-SCR and ADAPT-ENRICH), for analysis described in a separate protocol (ADAPT-BIE). Figure 1 depicts the study design and procedures.

Figure 1: Study Design and Procedures

*Images may be collected from FFDM and/or DBT performed on GE equipment prior to enrollment, if conducted within 30 days of each other.

** If rebiopsy is not recommended or if histopathology remains discordant with imaging findings after rebiopsy, the subject will be withdrawn from the study.

6.1.2. Study Design Details:

- Open-Label Interventions are known to researchers and subjects
- Blinded
- Double-Blinded

- | | | |
|--------------------------|-------------------------------------|---|
| Single-site |  | |
| Multi-site |  | Data will be pooled from multiple studies (e.g. ADAPT-SCR, ADAPT-BX, & ADAPT-ENRICH) at multiple sites |
| Randomization Procedure: |  | |
| Not randomized: |  | Treatments occur as clinically indicated, not according to randomization |
| Single arm |  | |
| Comparator |  | Diagnostic accuracy of DBT vs FFDM will be assessed in a separate protocol (ADAPT-BIE) |
| Parallel |  | |
| Crossover |  | This is a within-subject crossover study |
| Prospective |  | Subjects are enrolled and then undergo study procedures |

6.2. Study Timeframe

The study is expected to begin in the fourth quarter of 2014, and last for approximately two years (24 months), or until the target subject population is enrolled or the Sponsor otherwise indicates in writing that enrollment should be terminated. The end of the study shall be defined as the date when the last subject undergoes biopsy procedures and concordance is established, if applicable. Subject participation will be from the point of enrollment until truth determination of cancer status. The Investigator shall not begin the study until the applicable EC/IRB and necessary regulatory authority (when required) approval have been obtained.

6.3. Controls and Minimization of Bias

The following bias control methods are being employed in this study:

- a. Selection bias in allocating subjects to interventional groups will be limited by attempting to enroll consecutively eligible subjects. To reduce bias introduced from this study by subjects who are expected to be referred for biopsy primarily based on FFDM screening, other sources (e.g. ADAPT-ENRICH) may be pooled to include cancer cases reaching biopsy through a DBT screening program.
- b. Spectrum bias will be limited by using a population expected to be representative of the general population at the investigational site, without regard for race, or ethnicity.

7. STUDY SUBJECTS

7.1. Number of Subjects

Up to 275 subjects referred for breast biopsy (Enrollment ceiling per site will be 165 subjects) will be enrolled from three (3) centers located in the US and Europe (France) until at least 90 histopathology-confirmed cancers have been accrued. Enrollment will be closed once the required number of cancers has been histologically identified. Data will be pooled with other

sources to achieve the target number of positive and negative cancer cases, as described in Section 10.1.1 Sample Size Justification.

7.2. Subject Population

Study subjects will be adult women (≥ 30 years of age) clinically referred for breast biopsy due to abnormalities on routine screening Mammography, breast ultrasound (U/S), breast Magnetic Resonance Imaging (MRI) or Digital Breast Tomosynthesis (DBT); subjects must have been asymptomatic at the time of screening.

7.3. Protection of Vulnerable Subjects

This study does not intend to enroll vulnerable subject populations.

7.4. Procedures for Enrollment

All subjects must satisfy all the inclusion criteria and none of the exclusion criteria defined in the protocol. Subjects must sign and date the informed consent form prior to completing protocol specific procedures. The Investigator may discuss with the Sponsor any subject who does not strictly meet the inclusion/exclusion criteria but who is thought to be otherwise appropriate for the study; if the Sponsor and Investigator agree that inclusion of the subject would not affect the scientific or ethical aspects of the study, the Sponsor may provide a written exception for the subject. In this case, the details of the exception will be recorded on the Case Report Form (CRF). A subject will be considered enrolled when determined eligible and informed consent is signed, whether or not the subject undergoes study procedures.

7.5. Inclusion Criteria

Subjects may be included that meet the following criteria:

1. Women aged 30 years or older (≥ 30 years old);
2. Initially asymptomatic women who underwent routine bilateral screening FFDM, breast ultrasound (U/S), breast magnetic resonance imaging (MRI), and/or DBT, followed by diagnostic work-up showing one or more abnormalities and referred for breast biopsy^{1, 2};
3. Are able and willing to comply with study procedures;
4. Have signed and dated the informed consent form;
5. Documented as non-pregnant based on the investigator's medical judgment and in consideration of local clinical practice standards for evidence of non-pregnancy.

¹ Subjects who had screening DBT or screening/diagnostic FFDM imaging on non-GE equipment may be enrolled if they agree to undergo repeat imaging on a GE system; If the prior screening and diagnostic mammographic examinations were not conducted at the recruiting site, review of those images by the investigator must confirm that breast biopsy recommendation is warranted and GE access to the images in DICOM format must be granted

² Screening FFDM and DBT image acquisitions must be within 30 days of each other.

7.6. Exclusion Criteria

Subjects must be excluded from participating in this study if they meet any of the following criteria:

1. Have been previously included in this study;
2. Have undergone diagnostic or surgical intervention(s) or procedure(s) on either breast, including mastectomy and cytopunction, before study-related imaging;
3. Have breasts too large to be adequately positioned on 24 x 31 centimeter (cm) FFDM digital receptor without anatomical cut off during a DBT or FFDM examination;
4. Have participated in (within the prior 30 days), another trial of an investigational product expected to interfere with study procedures or outcomes;
5. Have breast implant(s);
6. Have reconstructed breast(s).

7.7. Screening Subjects for Enrollment

Subjects will be screened for recruitment from initially asymptomatic populations referred for breast biopsy due to imaging findings at each site, in accordance with local EC/IRB recruitment policy. Enrollment decisions will be based upon the Investigator's judgment. Final screening will include confirmation that each subject meets all inclusion and no exclusion criteria. All screening will be conducted in compliance with applicable laws, regulations, and standard procedures at the investigational site.

8. PROCEDURES FOR RESEARCH STUDY

All enrolled subjects will undergo the following procedures prior to receiving study-specific imaging (if required) and/or undergoing their clinically indicated biopsy procedure:

- A notation will be made in the subject's medical chart that the subject is participating in the clinical trial. Additionally, the notation should indicate that the subject had her questions answered, and that she read, signed and dated, and had been given a copy of the Informed Consent Form (ICF);
- Study entry criteria, demographic information (including age), relevant reproductive medical/surgical history such as oophorectomy, hysterectomy, or other reproductive surgeries and pregnancy/menopausal status will be reviewed;
- A subject number will be assigned.

There is no special subject preparation required to perform DBT or FFDM mammography.

8.1. Digital Breast Tomosynthesis (DBT) and Full Field Digital Mammography (FFDM) Examinations

Prior screening and/or diagnostic FFDM and/or DBT images will be collected from each subject's medical record. If necessary (e.g. because prior screening and/or diagnostic FFDM and/or DBT

mammography images/views are not available or were not collected with GE equipment), a subject may undergo study-specific FFDM and/or DBT imaging. Study-specific imaging will include a bilateral two-view (both CC and MLO views) FFDM and/or DBT performed using the GE FFDM and/or DBT system available at the site and according to the hospital's standard procedure.

Two-view DBT and FFDM image acquisition (both CC and MLO views) shall be performed within 30 days of each other, regardless if FFDM or DBT was performed before or after the patient agreed to participate in the study. Subjects requiring study-specific imaging will undergo the following procedures:

- Enter a changing room to prepare for their mammogram;
- Each subject of child-bearing potential will wear a lead apron or have equivalent shielding during the FFDM and/or DBT procedures;
- Undergo FFDM and/or DBT procedure(s);
- Will be monitored for AEs and SAEs from study-specific DBT and FFDM and will be recorded in the source documents and CRF. Device malfunctions shall be sent to the Sponsor as per Section 12.5 Management of Device Complaints.

All scanning should be performed within the standard range of scan parameters, as per the manufacturer-provided operator's manual(s) for GE FFDM and DBT devices. The scan operator should conduct DBT and FFDM exam according to the standard clinical practice at the site with consideration for:

- Subjects with large breasts, because perspiration under the breast can cause the skin to soften, and become paper-thin;
- Any condition that exists which may cause unusual discomfort or tearing of the skin, which could include telling the subject the importance of correct positioning. The subject should be positioned carefully to avoid any discomfort to abnormalities such as warts, scarring, or skin which is not intact;
- Warmth of the front part of the breast support, which can be warm to the touch, as it contains electronic components that generate heat;
- Positioning the breast properly in FFDM and DBT in the CC position, where it is essential that the breast is lifted away from the chest wall and gently pulled forward, in order to visualize the maximum amount of breast tissue.

8.2. Post-Mammography Procedures

The following assessments will be performed:

- DBT and FFDM images will be assessed at the study site by one or more MQSA-qualified radiologists, as per institutional standard practice;

- If clinically indicated based on imaging results, subjects will undergo biopsy or surgical intervention and breast tissue histopathological analysis, as per institutional standard practice.

The IDI MammoWorkstation permits 3-D-reconstruction and 2-D-reconstruction (V-Preview). The evaluating radiologist should use the image reconstruction views appropriate for diagnostic evaluation, per his or her medical judgment, and handle diagnostic evaluations in accordance with the standard of care at the investigational site.

8.2.1. On-Site Image Interpretation

DBT and FFDM images of all included subjects will be assessed at the study site by one or more MQSA-qualified radiologists on an IDI MammoWorkstation. The DBT results may result in a recommendation that additional breast lesions be biopsied (in addition to that/those already planned when the patient entered the study). If so, biopsy plans may be changed accordingly.

The results of DBT alone, however, will not be used as a basis to cancel plans for biopsy of any lesion.

The evaluating radiologist(s) at the site will record for each subject, the following parameters:

- Breast density (as defined by BI-RADS® density categories)
- Finding characteristics, to include breast laterality, lesion type, depth, quadrant and size. In the case of multiple findings, a maximum of three (3) most suspicious findings will be scored and localized.

8.2.2. Additional Diagnostic Imaging

If a subject is called back for further diagnostic assessment, the additional breast imaging that the subject undergoes will be recorded on the CRF.

8.3. Biopsy Procedures

Percutaneous and open surgical breast interventions will proceed as per standard of care at the recruiting site. The interpretation of the local pathologist will be recorded on the CRF.

If the subject does not complete the biopsy procedure as scheduled or if the biopsy procedure is not successful or produces indeterminate results that are not able to be resolved by clinically indicated procedures, such as repeat biopsy(ies), the subject will be withdrawn.

For benign/negative histopathology results, the site radiologist will review the subject's imaging and histopathology findings for concordance, per the site's standard of care, and results will be captured on a CRF. Histologic concordance with imaging for negative or benign lesions will be considered truth for non-cancer status. If surgical excision is recommended even after concordance between imaging and histopathology, the resulting histopathology from surgical excision may be collected as part of the study.

Subjects who have negative or benign histology findings that are discordant with imaging shall be followed-up per the site's standard of care. If rebiopsy is recommended, the histology findings and concordance assessment of the rebiopsy will be used to determine the subject's cancer status. If rebiopsy is not recommended or if histopathology remains discordant with imaging findings after rebiopsy, the subject will be withdrawn from the study.

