1. STUDY SYNOPSIS

Title of Study: Assessment of Diagnostic Accuracy and Performance of Digital Breast Tomosynthesis Compared to Mammography (ADAPT Trial)

ADAPT-BX. Recruitment Plan for Initially Asymptomatic Women Referred for Breast Biopsy (ADAPT-BX)

Protocol Number (Study Number): 124.03-2014-GES-0010

Investigators and Study Center(s): Up to 3 centers in the United States (US) and France (FR)

[name]
Gustave Roussy

Address: [name],
[name]
France
[contact]
E-mail: [contact]

[name]
Cooper Health - Cooper Breast Imaging Centers

Address: [name]
[name]
US
[contact]
E-mail: [contact]

[name]
Boca Raton Regional Hospital
Christine E. Lynn Women's Health and Wellness
Institute

Address: [name]
[name]
US
[contact]
E-mail: [contact]

Objective: The aim of this recruitment plan (ADAPT-BX) is to collect image and technical data on both digital breast tomosynthesis (DBT) and full-field digital mammography (FFDM), along with other subject data including histology results from biopsy specimen examination and cancer classification data from initially asymptomatic women referred for biopsy after recall from screening and diagnostic work-up. These data will be included in a subsequent and prospectively planned pooled analysis described in a separate protocol (ADAPT-BIE) examining superiority of DBT to FFDM for breast cancer diagnosis and other clinical performance measures.

Study Design: An open-label, multi-center, accrual study collecting DBT and FFDM images from up to 275 initially asymptomatic women aged ≥ 30 years referred for clinically indicated breast biopsy based on suspicious breast imaging results will be conducted. CC and MLO views from bilateral GE DBT and GE screening and/or diagnostic FFDM taken within a 30 day window of each other will be collected and assessed on-site by qualified radiologist(s) for clinical management purposes. Results of biopsy(ies) and histopathology, including lesion characteristics, will be recorded and considered as truth if positive for cancer status. Subjects with negative or benign histological findings will have their images and histopathology reviewed for concordance, per the site's standard procedures. Histologic concordance with imaging will be considered truth for non-cancer status.

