8.4. Follow-up Procedures

Results from surgical intervention and/or any additional follow-up resulting from biopsy(ies) (e.g., breast ultrasound or magnetic resonance imaging [MRI]) will be considered in determining truth of cancer status.

No additional follow-up appointments will be required for subjects that have completed biopsy/surgical intervention with positive findings or documented histologic concordance with imaging.

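### Section 8.3 makes excision histology after a concordant benign biopsy optional to collect, although 8.4 and 5.3.1 rely on surgical results for cancer status

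*Combined protocol and SAP*

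**What the plan says.** The primary endpoint (5.3.1) is each site's diagnosis of cancer status, "based on histology of biopsy/surgical findings and histologic concordance with imaging for benign lesions".

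Section 8.3 gives the working rules. For benign or negative results the site radiologist reviews imaging against histology, and "Histologic concordance with imaging for negative or benign lesions will be considered truth for non-cancer status". If excision is still recommended after concordance, "the resulting histopathology from surgical excision may be collected as part of the study". Earlier in 8.3, directly after a sentence covering percutaneous and open surgical interventions, it says: "The interpretation of the local pathologist will be recorded on the CRF".

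Section 8.4 states that results of surgery, or of further follow-up arising from biopsy, "will be considered in determining truth of cancer status". It then requires no more follow-up appointments for "subjects that have completed biopsy/surgical intervention with positive findings or documented histologic concordance with imaging".

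The synopsis says that biopsy and histopathology results "will be recorded and considered as truth if positive for cancer status". Section 6.2 adds: "Subject participation will be from the point of enrollment until truth determination of cancer status".

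For discordant benign results, 8.3 and the Figure 1 footnote make withdrawal depend on rebiopsy not being recommended, or on persisting discordance after rebiopsy. Section 8.6.1 says that it follows 8.3, but its first condition is that neither rebiopsy nor histopathology takes place.

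**The concern.** Cancer status is what this study delivers to the pooled reader study. Section 8.4 makes surgical results an input to that status, while 8.3 leaves one class of surgical result to the site's discretion. Two sites could each comply with 8.3, one retrieving the excision report and the other not, and label identical women differently.

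The error can go in one direction only. A cancer found at excision but not reported to the study stays in the non-cancer group. It is also missing from the count of histologically confirmed cancers that closes enrolment (7.1) and enters the accrual-based success criterion (10.4).

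**Working it through.** **Step 1. The passages side by side: concordant benign biopsy, then excision.**

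| Section | Role of the excision result |
|---|---|
| 8.3, concordance sentence | None needed; concordance already sets non-cancer truth |
| 8.3, excision sentence | Collection optional; no role in truth stated |
| 8.3, pathologist sentence | Recording required, if read to cover excision |
| 8.4 | Must be considered for truth; no exception for concordant cases |
| 5.3.1 | Surgical findings are part of the endpoint |
| Synopsis | Positive histopathology is cancer truth |

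If the pathologist sentence covers excision, 8.3 is at odds with itself. If it does not, 8.3 is at odds with 8.4 and 5.3.1.

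**Step 2. Does another section close the gap?** No. Section 6.2 ends participation at truth determination, which concordance can supply before any excision. Section 8.4 asks for no appointments after documented concordance. Section 15.3 allows the Sponsor to request biopsy results from the study period but does not require it.

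**Step 3. Which label results?**
- Excision benign: non-cancer, whether or not the report is collected.
- Excision positive, report collected: cancer (synopsis, 8.4).
- Excision positive, report not collected: non-cancer, by concordance.

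Only the third case gives a wrong label.

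**Step 4. Size.** The plan's own figure reproduces: 275 × 0.33 = 90.75, in line with the stated 90 non-cancer cases (10.1.1). The rest is assumption, because the documents give no rates. Treat the 90 as concordant benign. Let *e* be the share excised, *u* the share of those upgraded to cancer, and *n* the share of reports not collected. Then the number mislabelled is 90 × *e* × *u* × *n*.

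- Excised, *e* = 10% to 20%: 90 × 0.10 = 9 to 90 × 0.20 = 18.
- Upgraded, *u* = 5% to 20%: 9 × 0.05 = 0.45 to 18 × 0.20 = 3.6.
- Mislabelled, *n* = 100%: 0.45 to 3.6, or 0.5% to 4.0% of 90.
- Mislabelled, *n* = 50%: 0.225 to 1.8, or 0.25% to 2.0% of 90.
- Wider inputs, *e* = 5% to 30%, *u* = 2% to 20%, *n* = 100%: 90 × 0.05 × 0.02 = 0.09 to 90 × 0.30 × 0.20 = 5.4.

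**Step 5. Withdrawal wording for discordant benign results.**
- Rebiopsy not recommended and no tissue taken: both wordings withdraw the subject.
- Rebiopsy recommended but not done: 8.6.1 withdraws her. The discordance sentence in 8.3 is silent, although its rule on biopsies not completed as scheduled may apply.
- Rebiopsy not recommended but excision performed: the outcome depends on whether excision counts as rebiopsy, a term the protocol does not define.

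**The case against.** The best defence is that the sections do different jobs: 8.3 governs collection in one specific case, and 8.4 governs the use of results that are in hand. On that reading concordance is the intended endpoint, and 6.2 and the no-further-appointments sentence in 8.4 fit it. Appendix C also shows that the optional wording came in on purpose, when one-year follow-up was dropped. In addition, the pathologist sentence in 8.3 may already require the report.

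Part of this stands. The optional wording looks intended, and the reading softens the conflict. It does not remove it: 8.4 contains no limit to results in hand, and 5.3.1 names surgical findings without qualification. Relying on the pathologist sentence only moves the conflict inside 8.3.

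Three stronger readings are tempting but unsupported:
- A reader might infer that the truth rules compete, so that a known excision cancer could be classed as non-cancer. The synopsis treats positive histopathology as cancer truth, so the problem is incomplete collection.
- A reader might infer bias in the comparison of DBT with FFDM. This study tests no hypothesis. The comparison belongs to ADAPT-BIE, whose protocol and review charter are not among these documents and may set their own truth rules.
- A reader might infer from 8.6.1 that subjects are being wrongly withdrawn. The documents show a wording mismatch with few divergent cases and no more than that.

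**Conclusion.** The point holds and is minor. Followed as written, 8.3 can leave an excision-proven cancer labelled non-cancer, while 8.4 and 5.3.1 call for that result to count. The exposure is limited to reports not collected.

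The expected number is small: roughly 0.5 to 3.6 women of 90 if no report were collected, less if some are, and about 0.1 to 5.4 on wider inputs. These ranges rest entirely on assumed excision, upgrade and non-collection rates. They show the order of magnitude and are not estimates. No effect on the pooled analysis can be derived from these documents. The case for acting is that a primary endpoint should have one unambiguous rule and that the remedy costs little.

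The mismatch between 8.6.1 and 8.3 is a secondary, editorial point.

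**What to change.** These changes concern data capture and labelling only; care is unchanged.

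1. In 8.3, replace the optional wording with a requirement to collect excision histology wherever excision is performed. State that this histology is used in determining cancer status, consistent with 8.4 and 5.3.1.
2. In 6.2, let truth determination await an excision report that is already pending.
3. Reconcile the withdrawal wording in 8.3, the Figure 1 footnote and 8.6.1, and define whether excision counts as rebiopsy. Which rule applies is for the sponsor and investigators to settle.

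The textual conflict could instead be removed by limiting 8.4 to results in hand, with 5.3.1 aligned to match. That would leave uncollected cancers in the non-cancer group, so it is the weaker remedy.

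The cost is one wording amendment, retrieval of existing pathology reports (about 9 to 18 under the assumed 10% to 20% excision rate), and a few subjects kept open slightly longer.
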